Specific Aim #3:Establish the time needed to reach peak efficacy. Duration of treatment in the original study was three weeks, and significant therapeutic benefit was observed only at the three-week endpoint but not earlier. In the proposed study, subjects will receive study drug for 6 weeks and we expect that the size of the therapeutic benefit of oxytocin will increase from 3 to 6 weeks.

Specific Aim # 4: Investigate the possible cognitive effects of intranasal oxytocin. In the pilot study, oxytocin significantly improved short term recall performance in the California Verbal Learning Test. This raises the possibility that chronic oxytocin will improve cognitive deficits associated with schizophrenia. This study will test this hypothesis using the Computerized Multiphasic Interactive Neurocognitive DualDisplay™ System (CMINDS®) and Mayer-Salovey-Caruso Emotional Intelligence Test: Managing Emotions (MSCEIT™ ME).

Specific Aim #5: To determine if daily intranasal oxytocin is sufficiently safe, feasible and acceptable to patients to warrant further clinical development. Information derived from this study will inform development of oxytocin not only for schizophrenia but other potential neuropsychiatric disorders.

Specific Aim #6: The objective of the study is to compare the efficacy of intranasal oxytocin versus intranasal placebo to improve symptoms in schizophrenia patients who have residual symptoms despite being on adequate treatment with antipsychotic medication. Improvement will be measured by total score in the Positive and Negative Syndrome Scale (PANSS).

Specific Aim #7: To determine if oxytocin-induced enhancement of mu-rhythm suppression of 'mirror' neurons in schizophrenia patients can serve as a predictive biomarker of individual clinical response to this neurohormone.

Secondary objectives include:

 To evaluate the efficacy of intranasal Oxytocin as measured by change in the total CGI-Severity and Improvement scores

- To evaluate the efficacy of intranasal Oxytocin as measured by change in the total GAF score
- To evaluate the efficacy of intranasal Oxytocin as measured by change in the total scores of HAM-A.
- To evaluate the efficacy of intranasal Oxytocin on self-rated social anxiety as measured by change in the total Social Phobia Inventory (SPIN).
- To evaluate the efficacy of intranasal Oxytocin as measured by change in the total Calgary Depression Scale for Schizophrenia (CDSS) scores.

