Mu wave suppression paradigm: If subjects agree to participate in this sub-study, the informed consent for EEG collection will be obtained prior to any EEG procedures. EEG waves will be recorded over 32-sites using a standard 32-electrode cap with the Biosemi system (9), while subjects are watching 60-80 second videos. The videos will consist of experimental conditions (point light animations of biological and non-biological motion, scrambled condition) and baseline condition (2 moving balls). All videos will be presented twice, using Presentation software (10). Data from both trials will be combined prior to analysis. Filters will be set to automatically identify and block any segments with eye movements and body movements (using +/- 40 microvolt deviations). Data will only be analyzed if there is at least 2 minutes of clean EEG per condition. For each segment, integrated power in the 8–13 Hz range will be computed using a Fast Fourier Transform. Mu suppression will be calculated for central (C3, Cz and C4) and occipital (O1 and O2) sites using the equation: Mu suppression = log10 (mu power of experimental condition/ mu power of ball condition). Occipital site electrical discharges will be recorded, integrated for power and compared between groups to determine if posterior alpha activity is causing differences across conditions.

STUDY PROCEDURES

Visit	Screen	Baseline	Midweek	3	4	5	6	7	8/ET
Week	-1	0	0	1	2	3	4	5	6
Days	-7 to -1	0	3/4	7	14	21	28	35	42
General Procedures									
Informed Consent	Х								
Assess Inclusion/Exclusion	Х	Х		Χ	Х	Х	Х	Х	Х
Medical History	Х								
Physical Exam	Х								
SCID/Psychiatric History	Х								
Urine Drug Screen ^b	Х								
Urine Pregnancy Screen ^c	Х	Х							
Vital signs/ weight	Х	Х		Χ	Χ	Х	Х	Х	Х
Blood chemistryd/Urine osmolality	Х								Х
Oxytocin Levels ^e		XX							Х
EEG	XX								Х

Clinician-Rated Scales									
PANSS ^f	(x)	Х		Х	Х	Х	Х	Х	Х
HAM-A/ CDSS/ CGI:S ⁹ /									
CGI:I/ GAF		Х		Х	Χ	Х	Х	Х	Х
Cognitive tests (CMINDS® and									Х
MSCEIT [™] ME) ^h	Х	Х							
Patient-Rated Scales									
CTQ	Х								
TSQM		Х		Х	Х	Х	Х	Х	Х
PTS/ SPIN/ ASEX ⁱ /									
ER-40/ ECR		XX		Х	Х	Х	Х	Χ	Х
Other Procedures									
Mid-Week Safety Call ^j			Х						
Dispense study drug		Х		Х	Х	Х	Х	Х	
Single Challenge Dose ^k	Х								
Concomitant Meds		Х	Х	Х	Х	Х	Х	Х	Х
Adverse Events		Х	Х	Х	Х	Х	Χ	Х	Χ
1-hr safety monitoring following in-									
clinic dose		Х							

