h Practice improvement is expected with repetition of some MATRICS tests. While the parallel group design will determine any improvement beyond the practice effect, neuropsychologists [name] and [name] have pointed out the majority of practice effect occurs between the first and second administrations of the MATRICS battery (personal communications). This finding by [name] and [name] regarding paper versions of the MATRICS™ should translate to the computerized versions of the CMINDS® as O'Halloran et al. (2007) found that standard paper administration versions and computerized administration versions of neurocognitive assessment instruments are substantially equivalent. These computerized versions yielded highly equivalent measures of absolute agreement throughout all the test batteries when compared to the standard paper versions. The group comparison will be between baseline (after the majority of practice effect has occurred) and 6 weeks. While this strategy may miss transient improvement between these timepoints it will decrease the practice effect. Transient improvements in cognition are not clinically meaningful.

All patient-rated scales except the ASEX will also be given 50 minutes after the in-clinic dose at the Baseline Visit.

^jA Mid-Week Safety Call to Study Site - The subject will be instructed to contact study staff on day 3 or day 4 of taking study drug. This call will be a brief open ended question and answer discussion to find out the subject's experiences with the study medication over the past few days and answer any questions that may arise.

^kA challenge dose will be administered between screening EEG paradigms. This dose will only be administered after all other inclusion/exclusion criteria have been verified. All subjects will receive 24IU as a challenge dose.

Study Procedure Details

Visit 1 – Screening (approximately 4-5 hours)

During Visit 1 of the study the volunteer will:

- Be asked questions about medical and psychiatric history
- Participate in a clinical interview called a Structured Clinical Interview for DSM-IV-TR (SCID) which is a structured question and answer discussion. This will be performed by a trained study staff who will ask a series of questions about behaviors and mood symptoms over time
- Be given a physical examination by one of the study doctors
- Have weight, pulse and blood pressure measured

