- If the volunteer is a woman capable of having children, a urine test will be done to ensure she is not pregnant
- Give a urine sample for testing to make sure there are no illegal or controlled substances in his/her body. The results of any urine drug screen will remain confidential and be disclosed only as required by law
- Blood draw (about one teaspoon or 5 mL) and urine sample will be collected that will include standard tests to make sure volunteers are healthy
- Be asked questions about health and any current illnesses or medications (including over-the-counter medications, herbal remedies, alcohol consumption, and substances of abuse).
 Be asked a series of questions about how s/he was feeling within the past few weeks such as whether there were anxious feelings, feelings of depression or difficulty concentrating. The volunteer will also possibly be asked about symptoms that are commonly associated with schizophrenia using a clinical interview called the SCI-PANSS (Structured Clinical Interview Positive and Negative Syndrome Scale).

The SCI-PANSS will be completed at the discretion of the investigator if he feels that the subject may not met entry criteria

- Complete a series of activities which will be used to measure process of thought called the CMINDS® and MSCEIT™ ME
- Premenopausal women will be queried regarding their menstrual cycles and data correlated with clinical findings
- Once all inclusion/exclusion criteria have been met subjects will have a baseline EEG performed
- Subsequently subjects will receive a, one time, challenge dose of 24 or 48 IU oxytocin followed by the EEG paradigm

Visit 2-Baseline (approximately 2 hours)

During Visit 2 – Baseline, the volunteer will:

- Have weight, pulse and blood pressure measured
- Be asked questions about health and any current illnesses or medications (including over-the-counter medications, herbal remedies, alcohol consumption, and substances of abuse)
- Be asked a series of questions about how s/he was feeling within the past few weeks such as whether
 there were anxious feelings, feelings of depression or difficulty concentrating. The volunteer will also be
 asked about symptoms that are commonly associated with schizophrenia using a clinical interview called
 the SCI-PANSS (Structured Clinical Interview Positive and Negative Syndrome Scale)
- Complete a series of activities which will be used to measure process of thought called the CMINDS® and MSCEIT™ ME

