- Complete a questionnaire about symptoms of paranoia and sexual functioning
- Complete a test onability to recognize emotions called the Penn Emotion Recognition Test (ER-40).

Additionally at Visit 8 (week 6 or Early Termination);

- Complete a series of activities which will be used to measure process of thought called the CMINDS® and MSCEIT™ ME
- Have an additional blood sample taken (about 1 tablespoon) to monitor study drug levels in the blood
- EEG paradigm will be conducted

Follow Up Call

The volunteer will be asked to contact the study site one week after the last study drug dose to report taking any new medications or any unusual experiences since stopping the study drug.

Administration and dispensing of the study medication:

Except the one time challenge dose, this is a double-blind study, participants will be randomized to receive one of three possible intranasal study medications adjunctive to their antipsychotics: oxytocin 84 IU, oxytocin 168 IU or placebo (vehicle without oxytocin). Randomization will be performed stratifying gender groups, type of antipsychotic (typical versus atypical) and severity of symptoms based upon PANSS score (<90 versus >90) so that gender, symptom severity and antipsychotic type are distributed relatively evenly across treatment groups. Bottles containing placebo or two different concentrations of oxytocin will be formulated (See Study Drug Formulation below) so that the concentration of oxytocin in the high dose (168 IU) will be double that of the low dose (84 IU). All subjects will be instructed to spray 7 pumps of the spray bottle (one in each nostril, alternating nostrils) to achieve correct dose in the morning and again in the afternoon. Subjects will be given enough study drug at the time of the visit to last until the next visit with extra to cover approximately three additional days. Each pump bottle has 5 ml (300 IU) which is enough for 2.5 days of study drug. Therefore, subjects will be given one spray bottle supply at the time of each visit. The weight of each bottle will be recorded prior to dispensing. After all procedures are performed on baseline visit and study drug is randomly assigned, a dose of the study drug will be taken at the study site, in the presence of a staff member to insure correct administration.

Study Drug Compliance

- 1. Subjects will be instructed on proper use of the nasal device from study staff.

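### The single challenge dose is 24 IU in the schedule footnote but 24 or 48 IU in the Visit 1 text, and the Aim 7 mu-suppression analysis has no dose term

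*Combined protocol and SAP*

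**What the plan says.** All of the following is current text in the combined protocol and SAP.

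- **Section 9, study procedures table, footnote k.** The challenge is given between the screening EEG recordings, once eligibility is confirmed. The footnote ends: "All subjects will receive 24IU as a challenge dose".
- **Section 9, Study Procedure Details, Visit 1.** Subjects receive a one-time "challenge dose of 24 or 48 IU oxytocin", after which the EEG is repeated. Neither this section nor any other says who would receive 24 IU and who 48 IU.
- **Section 9, Mu wave suppression paradigm.** The EEG work is optional: "If subjects agree to participate in this sub-study, the informed consent for EEG collection will be obtained prior to any EEG procedures".
- **Section 9, Visit 1 and the table.** Visit 1 states "Once all inclusion/exclusion criteria have been met subjects will have a baseline EEG performed", with no opt-in condition. The table rows for EEG and for the challenge dose carry no sub-study marker.
- **Section 9, Administration and dispensing.** "Except the one time challenge dose, this is a double-blind study", so the challenge lies outside the blind.
- **Section 6, Specific Aim 7.** The aim is to learn whether oxytocin-induced enhancement of mu suppression "can serve as a predictive biomarker of individual clinical response to this neurohormone".
- **Section 9, Statistical Consideration, MU-Suppression.** The mu response to one dose of oxytocin is correlated with symptom severity after six weeks. Subjects are also split at the median into High and Low suppressors. A further correlation uses values after the single dose. No dose is named, and there is no dose covariate or stratum.

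**The concern.** The mu response to the challenge is the Aim 7 predictor, so the challenge is the stimulus that defines the biomarker. One place fixes that stimulus and another allows a two-fold range. Staff working from the table and staff working from the visit text could give different doses and both be following the protocol.

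If that happened, a subject could rank as a High suppressor because of a larger dose rather than a more responsive brain. The planned analysis could not separate the two.

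A smaller mismatch concerns who is challenged. Footnote k, the Visit 1 text and the table speak of subjects generally, while the paradigm description limits the EEG work to those who agree to it.

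**Working it through.** **1. Dose, side by side.** Footnote k: 24 IU, stated for all. Visit 1: 24 or 48 IU. Ratio: 48 / 24 = 2. The two statements are compatible only if 48 IU is never used, and no other section says so.

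**2. Share of predictor variance due to dose.** The documents give no dose-response of mu suppression to oxytocin and no split between doses, so both inputs are assumptions. Take half the subjects on each dose, a within-dose SD of 1 and a difference of g SD between dose means. The between-dose variance is g²/4, so

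share = (g²/4) / (1 + g²/4).

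If the outcome is unrelated to challenge dose, the pooled product-moment correlation equals the within-dose correlation times √(1 − share).

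| Assumed g | g²/4 | Share due to dose | √(1 − share) |
|---|---|---|---|
| 0, or one dose only | 0 | 0% | 1.00 |
| 0.2 | 0.01 | 0.01/1.01 = 1.0% | 0.995 |
| 0.5 | 0.0625 | 0.0625/1.0625 = 5.9% | 0.97 |
| 1.0 | 0.25 | 0.25/1.25 = 20% | 0.89 |

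At the upper end the correlation shrinks by about 11% in relative terms (1 − 0.89); at g = 0.5 it shrinks by about 3%.

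**3. Who is challenged.** Footnote k and Visit 1 both place the dose between EEG recordings, and the paradigm description makes those recordings opt-in. A subject without EEG has no such point in the visit. Read together, these places suggest that only EEG participants are challenged, and that the last sentence of footnote k means one dose for all of them. The sentence itself has no such limit.

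The reading changes a count. The plan has 24 placebo and 48 oxytocin subjects. Let f be the fraction of the placebo arm who are challenged (not given in the documents). The number with at least one oxytocin dose, which is how the Safety Endpoints text defines the safety dataset, is 48 + 24f: 60 at f = 0.5, and 72 if all are challenged.

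**4. Primary comparison.** Neither the dose conflict nor the opt-in mismatch enters the PANSS sample size calculation or its alpha.

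**The case against.** The best reply is that the challenge is defined by its place in the EEG procedure. On that view nobody outside the sub-study is dosed, and what is missing is a qualifier. This largely stands.

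A reader might infer from the words of footnote k that the exposed group is undefined, or that subjects without EEG, including later placebo subjects, take unblinded oxytocin from which no data are obtained. The documents do not support that. No section says that subjects without EEG are dosed, and the reading requires detaching the footnote's last sentence from its first. The wording still conflicts literally with the opt-in condition and needs aligning.

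The second reply is that any figure for the effect of mixed doses is assumed. That also stands. A reader might quote 6-20% of predictor variance as the damage, but those values start from an assumed shift of at least 0.5 SD. A smaller shift, or use of one dose only, brings the figure to or near zero.

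The third reply is that this concerns one correlational aim in an optional part of a pilot study. That is true and limits the weight of the point. It does not remove the contradiction: none of these replies explains the 48 IU option in the Visit 1 text.

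**Conclusion.** The plan is wrong as written on the challenge dose. Footnote k and the Visit 1 text disagree by a factor of two, no rule resolves them, and the Aim 7 analysis would not detect or correct a mixture.

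The statistical effect is conditional. It is nil if one dose is used. If both are used, about 0-20% of the variance in the predictor would reflect dose, given the assumed equal split and a shift of 0-1 SD. The matching attenuation of a correlation is 0-11%, if the outcome is unrelated to challenge dose. If dose followed site, calendar time or severity, the bias could go in either direction; the documents do not allow that to be sized.

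The mismatch over who is challenged is secondary: a missing sub-study qualifier, with a likely but unstated meaning. A reader might go further and infer that the main efficacy result is undermined. The documents do not support this: the sample size and alpha of the PANSS comparison do not depend on the challenge.

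**What to change.** Reconcile footnote k, the Visit 1 text, the table rows and the Mu wave suppression paradigm text to one statement of the challenge dose and one of who receives it. Which dose and which group are right is for the sponsor to state.

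Name the challenge dose in the MU-Suppression analysis text. If more than one dose was or will be given, use the recorded dose as a covariate or stratum: compute the correlations within or adjusted for dose, and take the High/Low median within dose.

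The cost is a few lines of protocol and analysis wording. The case report forms are not among the documents, so whether the dose given is already captured is unknown; if it is not, one data field is needed.

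No change to the sample size or the primary analysis is required.

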- 2. Subjects will be given a diary card by the study staff to mark each use of the study drug in between site visits to the study site. This is to help subjects track study drug use. Subjects will be instructed to return study drug nasal spray bottles, used or unused, to the site at each visit along with the diary card.
- 3. Each bottle will re-weighed after return to estimate the amount of fluid remaining

STUDY DRUG:

Intranasal oxytocin is FDA approved as a lactation aid and was commercially marketed (Syntocinon®, Novartis) in the US up to the 1990's. It continues to be marketed commercially by Novartis in Europe and elsewhere. Oxytocin powder (Pictocin, Novartis) is readily available in the US and is used for intravenous

administration as a paruition stimulant in pregnant women. Both intravenous and intranasal oxytocin are well tolerated and safe (Hoover RT 1971) (see risk section of this Research Plan).

This study will use oxytocin powder supplied by Spectrum Laboratories and UCSD Investigational Drug Service (IDS) will make formulate both the Oxytocin and Placebo.

-Chlorbutanolhemihydrat 2.5mg -Methyl-4-hydroxybenzoat 0.4mg -Propyl-4-hydroxybenzoat 0.2mg -Dinatriumphosphatanhydricum 1.9mg -Acidumcitricumanhydricum 2.56mg 5.0mg -Na-Sorbit -Sorbitol 70% 25.0 mg -Glycerin 85% 25.0mg -Aqua pur. q.s.

Comment: 1 IU is 1.7 micrograms oxytocin and 1 puff is 12 IU (=20.4 micrograms oxytocin)

STATISTICAL CONSIDERATION

Our primary analysis will be the comparison of subjects on oxytocin with subjects on placebo using a mixed model repeated measures analysis (MMRM). If this comparison is statistically significant then we use a linear contrast to investigate the dose-response between 84 IU (42 IU bid) and 168 IU (84 IU bid). We also have introduced an adaptive design that is consistent with FDA guidance for phase 2 studies when dosing groups are unclear (2010).

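### The dispensing rule asks for about 10 days of drug per visit, but its bottle figures cover at most 3.57 days and the number of bottles is not clearly stated

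*Combined protocol and SAP*

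**What the plan says.** Section 4, the Overview in section 9 and Statistical Consideration agree on the doses: 84 IU/day and 168 IU/day, and where the split is given it is 42 and 84 IU twice daily. Visits are weekly.

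Administration and dispensing of the study medication (section 9) then sets these rules:

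- Pumps: "All subjects will be instructed to spray 7 pumps of the spray bottle", in the morning and again in the afternoon.
- Concentrations: "the concentration of oxytocin in the high dose (168 IU) will be double that of the low dose (84 IU").
- Supply: each visit must provide enough drug "to last until the next visit with extra to cover approximately three additional days".
- Bottle: "Each pump bottle has 5 ml (300 IU) which is enough for 2.5 days of study drug".
- Conclusion: "Therefore, subjects will be given one spray bottle supply at the time of each visit".

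Under Study Drug there is one puff strength, with no arm named: "Comment: 1 IU is 1.7 micrograms oxytocin and 1 puff is 12 IU (=20.4 micrograms oxytocin"). Under Study Drug Compliance, subjects return "nasal spray bottles, used or unused" at each visit, and "Each bottle will re-weighed after return to estimate the amount of fluid remaining".

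**The concern.** The supply sentence and the bottle sentence stand in one paragraph, joined by a therefore, and the conclusion does not follow. A bottle said to last 2.5 days is offered as the reason why one bottle supply meets a need of about 10 days. The bottle sentence also gives a single content for a product that the same paragraph says is made in two concentrations.

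The drug is compounded locally by the investigational drug service, so no commercial label fills the gap. If staff took the rule literally, fully adherent subjects would have no drug for much of each week. Every returned bottle would be empty, so its weight could not separate a subject who used all of the week's drug from one who stopped when the bottle ran dry.

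**Working it through.** **Inputs.** Doses of 42 and 84 IU twice daily (section 4); 7 pumps twice daily in every arm, a 2:1 concentration ratio, 5 ml, 300 IU, 2.5 days, and supply to the next visit plus about 3 days (Administration and dispensing); 7 days between visits (section 4); 12 IU per puff and 1.7 micrograms per IU (Study Drug).

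**Puff strength.** The printed conversion reproduces: 12 × 1.7 = 20.4 micrograms.

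- High arm: 84 / 7 = 12 IU per puff; 12 × 14 = 168 IU/day. The printed figure fits.
- Low arm: 42 / 7 = 6 IU per puff; 6 × 1.7 = 10.2 micrograms; 6 × 14 = 84 IU/day. This strength is not printed.

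**Days per bottle.** The printed 2.5 days does not reproduce as a bottle's duration at either dose.

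- 300 / 168 = 1.79 days.
- 300 / 84 = 3.57 days.
- 300 / 2.5 = 120 IU/day, which is neither study dose.
- Other readings do not give 2.5 either. The mean dose of 126 IU/day gives 300 / 126 = 2.38 days. One dose a day gives 300 / 42 = 7.14 or 300 / 84 = 3.57 days.

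**Pumps per bottle and bottles needed.** Need to the next visit: 7 × 14 = 98 pumps. Need for about 10 days: 10 × 14 = 140 pumps. The 5 ml fill is taken as equal across strengths, as printed. Equal pump volume follows from equal pump counts with a 2:1 dose ratio and a 2:1 concentration ratio.

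| Reading | Content low / high | Pumps per bottle | Days per bottle | Share of 98 pumps from one bottle | Bottles for 140 pumps |
|---|---|---|---|---|---|
| 300 IU is the high strength | 150 / 300 IU | 300/12 = 25 | 25/14 = 1.79 | 25/98 = 26% | 5.6, so 6 |
| 2.5 days is right, 300 IU is not | 210 / 420 IU | 2.5 × 14 = 35 | 2.5 | 35/98 = 36% | 4 |
| 300 IU is the low strength | 300 / 600 IU | 300/6 = 50 | 50/14 = 3.57 | 50/98 = 51% | 2.8, so 3 |

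The middle row's contents are 35 × 6 = 210 and 35 × 12 = 420 IU.

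**Could one 5 ml bottle reach the next visit?** It would have to give 98 pumps of 5 / 98 = 0.051 ml. The figures as printed imply 5 / 25 = 0.2 ml, 5 / 35 = 0.143 ml or 5 / 50 = 0.1 ml. None is that small.

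**The case against.** The strongest reply is that the governing sentence already requires enough drug for the interval plus a margin, and that a bottle supply can mean a set of bottles. The compliance text supports this: subjects return bottles in the plural, some unused, and an adherent subject could hardly return an unused bottle after receiving only one. This stands. It makes the run-out conditional, and it leaves the number of bottles unstated.

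A second reply is that enough for 2.5 days may be a loose minimum. If 300 IU is the low strength, a bottle gives 50 pumps and 2.5 days uses 35, leaving 15. This also stands, so the 2.5 days is not false on every reading. It does fail if 300 IU is the high strength, and the text does not say which applies. Nor can 300 IU be meant literally for every bottle, since placebo contains no oxytocin.

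Third, the 12 IU comment contains no arithmetic error. The 2:1 rule lets a reader derive 6 IU for the low arm, so only a label is missing. That is correct.

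Fourth, the analysis sections use neither bottle weight nor compliance, and the primary population is all randomized subjects. This limits the consequence to drug supply and adherence monitoring.

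**Conclusion.** The dispensing paragraph is inconsistent and should be corrected; the severity is minor to should-fix. Read as one bottle per visit, the rule covers 26% to 51% of the pumps needed to the next weekly visit, and 36% on the printed 2.5 days. Read as a set, it omits the count, which is 3, 4 or 6 bottles for about 10 days depending on which printed figure is right. The sizes assume equal 5 ml fill, equal pump volume and full adherence.

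Two stronger readings are tempting. A reader might infer that the low arm would be filled at 12 IU per puff, receive 168 IU/day and lose the dose contrast. The documents do not support that: the two doses are stated consistently in several places, and the paragraph itself requires half the concentration in the low arm. A reader might also infer that subjects will certainly run out of drug. That holds only under the one-bottle reading, which contradicts the paragraph's own supply requirement. Sample size and analysis are not affected.

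**What to change.** **Administration and dispensing of the study medication.** Replace the bottle sentence with IU per bottle and pumps per bottle for each strength, as confirmed by the pharmacy. Replace the one-bottle wording with the number of bottles that delivers at least 140 pumps, the same in all three arms so that the count does not reveal the arm: 3 if a bottle gives 50 pumps, 4 if it gives 35, 6 if it gives 25. Leave pump volumes out until the pharmacy confirms them, because the values above are only back-calculated from the figures in dispute.

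**Study Drug.** Label 12 IU per puff (20.4 micrograms) as the high strength and add 6 IU per puff (10.2 micrograms) as the low strength.

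**Cost.** A wording amendment and one pharmacy check. If one bottle per visit was really planned, 2 to 5 more bottles per subject per visit are needed (3 − 1 to 6 − 1). Doses, pump counts, visits and analysis stay as they are.
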